7.3. Assessment of Safety Syringe Use

At Visit 2 (Week 0), and at Visit 4 (Week 8), the investigator or designee will observe, using a checklist based on the safety syringe IFU, the ability of the subject/caregiver to (self)-administer the injection. The Observer Checklist (see SRM) will be used to determine if each step, according to the IFU, was completed easily, with some difficulty or not completed/intervention required. Failure to perform one of the critical steps, i.e., correct choice of injection site and a full dose administered (determined by the subject fully inserting the needle, slowly depressing the plunger until the stopper reaches the bottom of the syringe and activating the needle guard by moving the thumb up) will be deemed to be a failure to successfully administer the injection. In addition, the investigator will be asked to inspect the safety syringe, following each injection, to confirm that the white plunger has been pushed all the way down and the needle has retracted up into the syringe body, as well as noting any additional observations which indicate the full dose has not been dispensed.

Any user errors or device malfunctions will be recorded and reported using the Safety Syringe Error/Failure Reporting Form (see SRM). Malfunction or failure of the safety syringe meeting the definition of a Medical Device Incident (see [Appendix 5](#)), will also require a Medical Device Incident form to be completed and must be reported as described in Section [7.7.3](#).

Subjects will complete a patient diary at Week 0, 4 and 8 recording the pain experienced immediately following, 1- and 24-hour after the injection (see SRM). At Week 4, when self-administration is performed outside the clinic (within 24-hours of attending the Visit 3 clinic visit), the subject/caregiver will also record the date and time of injection, site of injection, who administered the injection (subject or caregiver) and complete a checklist similar to the Observer Checklist outlining the various steps in the IFU and whether each step was completed easily, with some difficulty, or not completed (see SRM). The responses on the checklist will be checked by the Investigator or designee at the next clinic visit (Visit 4). Failure to perform one of the critical steps will be deemed to be a failure to successfully administer the injection.

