2.2. Study Objective(s) and Endpoint(s)

Objectives	Endpoints
Primary Objectives	Primary Endpoint

 To assess the use of the combination product, mepolizumab liquid drug product in safety syringe, for the subcutaneous self-administration of mepolizumab by subjects with severe eosinophilic asthma. 	
 Proportion of subjects successfully able to self-administer their observed third dose at Week 8.
Secondary Objectives	Secondary Endpoints

 To assess the use of mepolizumab liquid drug product in safety syringe outside the clinic setting. 	
 Proportion of subjects successfully able to self-administer their unobserved second dose outside the clinic setting at Week 4
Other Objectives	Other Endpoints

 To assess the use of mepolizumab liquid drug product in safety syringe both inside and outside of the clinic setting. 	
 Proportion of subjects successfully able to self-administer their observed first dose at Week 0 Proportion of subjects successfully able to self-administer both their unobserved second dose and observed third observed dose at Weeks 4 and 8 Proportion of subjects successfully able to self-administer all three doses at Weeks 0, 4 and 8

 To evaluate safety syringe use & functionality. 	
 Device usability/functionality questionnaire completed at the End of Study/Early Withdrawal Visit

 To evaluate any safety syringe injection errors/failures related to use or device performance. 	
 Investigator evaluation of user/device errors Root cause analysis of each unsuccessful injection

 To characterise the subject experience of using the mepolizumab liquid drug product in safety syringe. 	
 Subject Exit Interviews completed over the telephone after the End of Study/Early Withdrawal Visit

Objectives	Endpoints

 To assess mepolizumab plasma trough concentrations (C_{trough}) following the SC administration of mepolizumab liquid drug product in safety syringe. 	
 Mepolizumab plasma C_{trough} at Weeks 4, 8 and 12

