7.2. Other Analyses to Evaluate Safety Syringe

The following endpoints will be summarised in the same way as the primary endpoint (Section 7.1).

- The number and percentage of subjects successfully able to self-administer their unobserved second dose at Week 4. The denominator for the percentage calculation will be the number of subjects attempting an injection at Week 4.
- The number and percentage of subjects successfully able to self-administer their observed first dose at Week 0. The denominator for the percentage calculation will be the number of subjects attempting an injection at Week 0.
- The number and percentage of subjects successfully able to self-administer both their unobserved second dose at Week 4 and their observed third dose at Week 8. The denominator for the percentage calculation will be the number of subjects attempting an injection at both Week 4 and Week 8.

- The number and percentage of subjects successfully able to self-administer all three doses at Week 0, 4 and 8. The denominator for the percentage calculation will be the number of subjects attempting all three doses at Week 0, 4 and 8.

Table 3 provides an overview of the analyses to evaluate the safety syringe, with full details of data displays being presented in Appendix 8: List of Data Displays.

Table 3 Overview of Analyses to Evaluate Safety Syringe

	Summary		Individual	
	T	F	F	L
Primary Endpoint				
Proportion of subjects successfully able to self-administer their observed third dose at Week 8.	Y			Y
Secondary Endpoint				
Proportion of subjects successfully able to self-administer their unobserved second dose at Week 4.	Y			Y
Other Endpoint				
Proportion of subjects successfully able to self-administer their observed first dose at Week 0.	Y			Y
Proportion of subjects successfully able to self-administer their unobserved second dose at Week 4 and their observed third dose at Week 8.	Y			Y
Proportion of subjects successfully able to self-administer all three doses at Week 0, 4 and 8.	Y			Y
Investigator assessment of user/device errors by visit	Y			Y
Observer checklist for in-clinic injections	Y			Y ¹
Subject completed checklist for home injection	Y			Y ¹
Device usability/functionality subject completed questionnaire	Y			

NOTES :

- T = Table, F = Figure, L = Listing, Y = Yes display generated.
- Summary = Represents TFL related to any summaries (i.e. descriptive statistics) of the observed raw data.

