14.8.2. Evaluation of Safety Syringe

No.	Population	IDSL / TST ID / Example Shell	Title	Programming Notes	Deliverable [Priority]
Evaluation of Safety Syringe - Tables					
7.1	All Subjects	TAB_INJ1	Summary of the Proportion of Subjects Successfully Able to Self-Administer Injection by Visit		SAC
7.2	All Subjects	TAB_INJ2	Summary of Investigator Evaluation of User/Device Errors by Visit		SAC
7.3	All Subjects	TAB_INJ3	Summary of Observer Checklist for In-Clinic Injections		SAC
7.4	All Subjects	TAB_INJ4	Summary of Subject Completed Checklist for At-Home Injection at Week 4		SAC
7.5	All Subjects	TAB_INJ5	Summary of Device Usability/Functionality Questionnaire		SAC

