userid: /arenv/arprod/compound/study/final/drivers/drivername.sas DDMMYYYY HH:MM

Example TAB_INJ1
Protocol: MID205667
Population: All Subjects (Safety)

Table X
Summary of Proportion of Subjects Successfully Able to Self-Administer Injection by Visit

Visit	Liquid Safety Syringe (N = XX)		
	Attempted Injections	Successful Injections [1]	
	n (%)	n (%)	95% CI
WEEK 0	XX (XX%)	XX (XX%)	(XX%, XX%)
WEEK 4	XX (XX%)	XX (XX%)	(XX%, XX%)
WEEK 8	XX (XX%)	XX (XX%)	(XX%, XX%)
WEEK 4 and 8	XX (XX%)	XX (XX%)	(XX%, XX%)
WEEK 0, 4 and 8	XX (XX%)	XX (XX%)	(XX%, XX%)

[1] The denominator for the percentage of successful injections is the number of attempted injections.

CONFIDENTIAL

205667

Example TAB_INJ2
 Protocol: MID205667
 Population: All Subjects (Safety)

Page 1 of 1

Table X.X
 Summary of Investigator Evaluation of User/Device Errors by Visit

Visit	n		Liquid Safety Syringe (N=XX)
WEEK 0	XX	Was the drug successfully injected?	
		Yes	XX (XX%)
		No	XX (XX%)
		Not attempted	XX (XX%)
		User Error	
		Any User Error	XX (XX%)
		Ring cap not removed from autoinjector	XX (XX%)
		Autoinjector not properly activated on injection site (e.g., gold needle guard not flush with skin)	XX (XX%)
		Autoinjector used upside down	XX (XX%)
		Autoinjector pulled away before end of injection (i.e., before purple indicator stopped moving)	XX (XX%)
		Other	XX (XX%)
		Device Error	
		Any Device Error	XX (XX%)
		Autoinjector leaking	XX (XX%)
		Components missing / broken / cracked	XX (XX%)
		Inspection window not clear	XX (XX%)
		Cannot remove ring cap	XX (XX%)
		Bent needle	XX (XX%)
		Cannot push the gold needle guard down to activate (i.e., force too high)	XX (XX%)
		Autoinjector does not activate (after pressing gold needle guard down)	XX (XX%)

Programming Note: Continue for Week 4 and 8

userid: /arenv/arprod/compound/study/final/drivers/drivername.sas DDMMYYYY HH:MM

Example TAB_INJ3
 Protocol: MID205667
 Population: All Subjects (Safety)

Table X.X
 Summary of Observer Checklist for In-Clinic Injections

Visit: WEEK 0

Liquid Safety Syringe
 (N=XX)

Time from removal of syringe from storage to injection (mins)	n	XX
	Mean	XX.X
	SD	XX.XX
	Median	XX.X
	Minimum	XX
	Maximum	XX
Confirm who will be administering the injection	n	XX
	Patient	XX (XX%)
	Caregiver	XX (XX%)
Subject/caregiver completed all the training required	n	XX
	Yes	XX (XX%)
	No	XX (XX%)
Subject/caregiver had instructions for use (IFU) available for review during injection (as recommended)	n	XX
	Yes	XX (XX%)
	No	XX (XX%)

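### The SAP shell for the user/device-error table (TAB_INJ2, Table 7.2) lists autoinjector error categories in a safety-syringe study

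*SAP*

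**What the plan says.** SAP Section 2.2 includes "Investigator evaluation of user/device errors" among the Other endpoints. Table 3 in SAP Section 7.2 plans a table and a listing for it ("Investigator assessment of user/device errors by visit"). The list of displays in SAP Section 14.8.2 makes this Table 7.2, "Summary of Investigator Evaluation of User/Device Errors by Visit", and points to shell TAB_INJ2 with no programming note. Appendix 9 is therefore the only place in the SAP that sets out the table's error categories.

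Under a column headed for the liquid safety syringe, the user-error block of that shell starts with "Ring cap not removed from autoinjector" and includes "Autoinjector pulled away before end of injection (i.e., before purple indicator stopped moving)". The device-error block includes "Cannot push the gold needle guard down to activate (i.e., force too high)" and ends with "Autoinjector does not activate (after pressing gold needle guard down)". The user-error block closes with an Other row; the device-error block has none. A programming note inside the shell repeats the same rows for Weeks 4 and 8.

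Protocol Section 7.3 describes a different device. Its critical steps are "correct choice of injection site and a full dose administered (determined by the subject fully inserting the needle", followed by depressing the plunger fully and activating the needle guard by moving the thumb up. The investigator must also inspect the used syringe and confirm that the needle has retracted.

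**The concern.** The table is meant to show, visit by visit, which errors occurred and whether the investigator put them down to the user or to the device. A ring cap, a gold needle guard pressed against the skin and a purple indicator are not how this SAP's other shells or the protocol describe the safety syringe. If the shell is followed literally, most of its rows cannot be filled, some real syringe errors have no row of their own, and a syringe leak is reported under the name of another device. Protocol Section 9.4.1 also promises a by-visit summary of device-related issues that prevent a full dose, and TAB_INJ2 is the only SAP summary table with device-error rows.

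**Working it through.** The plan states no figure to reproduce. The check is a row count in TAB_INJ2, followed by a comparison with the protocol and the neighbouring shells.

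**Row count.** The two Any-error totals and the user-error Other row are left out.

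| Block | Named rows | Contain the word autoinjector | Name only an autoinjector part | Device-neutral | Other row? |
|---|---|---|---|---|---|
| User error | 4 | 4 | 0 | 0 | yes |
| Device error | 7 | 2 (leaking; not activating) | 2 (ring cap; gold needle guard) | 3 (components; inspection window; bent needle) | no |
| Total | 11 | 6 | 2 | 3 | |

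Autoinjector wording: 6 + 2 = 8 of 11, or 73%. On the literal word alone it is 6 of 11. Counting the two part-name rows is fair, because the same shell ties both parts to the autoinjector, while the syringe shells speak of a clear needle cap and of a guard released by lifting the thumb.

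**Comparison with Protocol Section 7.3.**

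- *Wrong injection site:* no named user-error row. It would go to Other.
- *Incomplete dose:* the row for withdrawing the device too early is a rough analogue, but it is defined by the purple indicator and not by needle, plunger or stopper. This is a wording defect more than a missing category.
- *Needle-guard or retraction failure of the device:* no row describes a syringe guard or retraction failure, and there is no Other row. It would appear only in the Any Device Error total.
- *Leak:* a row exists, but it names the autoinjector.

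**Comparison with LIST_INJ1.** This is the companion listing of the same investigator assessment, and its shell shows three example errors. Broken or cracked components have a TAB_INJ2 row as worded; a leaking syringe has one only after relabelling; a wrong site (arm) has none. That is 1 + 1 + 1 = 3.

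**What other displays still show.**

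- Table 7.3 (TAB_INJ3, Weeks 0 and 8) and Table 7.4 (TAB_INJ4, Week 4) count non-completion of the needle-insertion step (combined with pinching the skin), the plunger step and the thumb-up step, all in syringe terms.
- Table 6.8 gives injection site by visit. It does not split upper arm by who injected, although that site is correct only for a caregiver.
- Listing 7 gives injection site, Listing 8 the injector and Listing 15 the user or device error for each injection.
- Protocol Section 9.4.1 has Device Engineering summarise the root cause of every unsuccessful injection for the study report.
- TAB_INJ1, which carries the primary and secondary proportions and their confidence intervals, does not use these categories.

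**The case against.** The strongest reply is that little is lost. Appendix 9 is titled as example shells. LIST_INJ1 uses syringe wording, which suggests that the collected categories may already be those of the syringe; a programmer working from such data would find nothing to put in the ring-cap or purple-indicator rows and would query them. Site and step completion are tabulated at all three visits elsewhere. The study is descriptive, and this is an Other endpoint.

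Most of this stands, and it sets the size of the point. It does not remove it. Tables 7.3 and 7.4 record whether a step was completed, by an observer or by self-report at home; they do not give the investigator's attribution to user or device, which is what the endpoint asks for. Table 6.8 cannot tell a caregiver's correct use of the arm from a subject's incorrect use. No summary table names a guard or retraction malfunction.

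A reader might infer more than the documents support:

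- *That critical-step failures would be invisible by visit.* Tables 6.8, 7.3 and 7.4 contradict this, with the limits just given.
- *That errors were collected on autoinjector categories.* The eCRF and the Safety Syringe Error/Failure Reporting Form were not among the documents reviewed, so this is unknown.
- *That the shell was carried over from the separate autoinjector study.* The protocol's amendment log mentions such a study, but nothing states where the shell came from.

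**Conclusion.** The shell is wrong as written, and the correction is minor. Eight of 11 named rows describe another device. The clear category gaps are three: a wrong-site user-error row, a needle-guard or retraction device-error row, and an Other row under Device Error. The effect is limited to the user-versus-device breakdown in Table 7.2, repeated at three visits. The Any User Error and Any Device Error totals remain usable, and the primary and secondary results do not change.

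The mismatch in wording is certain from the text. The consequence rests on one assumption, that Table 7.2 is programmed as the shell shows. How a particular error would be tabulated also depends on the eCRF code list, which could not be checked.

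**What to change.** 1. Replace the TAB_INJ2 rows with the safety-syringe error categories collected on the eCRF and the Safety Syringe Error/Failure Reporting Form, in wording consistent with LIST_INJ1.
2. Include rows for incorrect injection site, incomplete dose (needle or plunger), and needle-guard or retraction failure.
3. Add an Other row under Device Error.
4. Before database freeze, confirm that the eCRF code list is the syringe version.

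The cost is one revised shell and one code-list check. If the code list lacks a needed category, a few error records may have to be recoded from their recorded text, where such text was collected.

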Three doses of mepolizumab liquid drug product in safety syringe will be self-administered by the subject/caregiver at 4-weekly intervals; 2 doses will be administered under observation in the clinic (at Visits 2 and 4). The second in clinic administration (Visit 4) will not include any onsite training or support, other than the IFU, which could assist the subject. One dose will be administered outside the clinic and without observation (within 24 hours after attending the clinic for Visit 3). Following each injection, subjects will complete a patient diary, included in the Study Reference Manual (SRM), and report the pain experienced immediately following, 1- and 24-hours post injection. Observations about the injection will be recorded by the investigators for the doses administered in the clinic using an observer checklist. For the unobserved dose administered at home, a similar checklist detailing the steps required to successfully administer the injection will be completed by the subject/caregiver. All injections will be assessed by the investigator for success based on:

- Direct observation of the self-administration using the investigator Observer Checklist if the mepolizumab dose was administered in the clinic, and inspection of the safety syringe
- Subject/caregiver completed checklist and inspection by the investigator of the returned safety syringe if the mepolizumab dose was administered outside the clinic

A self-administered injection is considered successful if the following criteria are met:

- Use of a correct injection site (abdomen/thigh or upper arm [caregiver only])
- Full dose administered: subject fully inserts the needle, slowly depresses the plunger until the stopper reaches the bottom of the syringe and activates the needle guard by moving the thumb up
- No observations are made with respect to the safety syringe, following inspection by the investigator, which indicates the full dose has not been dispensed

If the above criteria are met, the investigator will confirm the injection was successfully delivered.

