[1] Subject / caregiver completed task easily without repeated reference to the IFU.

[2] Subject / caregiver completed task but with some difficulty or repeated reference to the IFU for assistance.

[3] Subject / caregiver was not able to (or did not) complete task after multiple attempts and reference to the IFU, or intervention was required.

userid: /arenv/arprod/compound/study/final/drivers/drivername.sas DDMMYYYY HH:MM

Example TAB_INJ3 (cont.)
 Protocol: MID205667
 Population: All Subjects (Safety)

Table X.X
 Summary of Observer Checklist for In-Clinic Injections

Visit: WEEK 0

		Liquid Safety Syringe (N=XX)
Check that the subject / caregiver looks at the label to check the expiration date on the syringe prior to use.	n	XX
	Easily [1]	XX (XX%)
	With some difficulty [2]	XX (XX%)
	Did not complete [3]	XX (XX%)
Check that the subject / caregiver looks in the inspection window to check the liquid prior to use.	n	XX
	Easily [1]	XX (XX%)
	With some difficulty [2]	XX (XX%)
	Did not complete [3]	XX (XX%)

[1] Subject / caregiver completed task easily without repeated reference to the IFU.

[2] Subject / caregiver completed task but with some difficulty or repeated reference to the IFU for assistance.

[3] Subject / caregiver was not able to (or did not) complete task after multiple attempts and reference to the IFU, or intervention was required.

userid: /arenv/arprod/compound/study/final/drivers/drivername.sas DDMMYYYY HH:MM

Example TAB_INJ3 (cont.)
 Protocol: MID205667
 Population: All Subjects (Safety)

Table X.X
 Summary of Observer Checklist for In-Clinic Injections

Visit: WEEK 0

		Liquid Safety Syringe (N=XX)
Check that the subject / caregiver removes the clear needle cap from the safety syringe prior to use.	n	XX
	Easily [1]	XX (XX%)
	With some difficulty [2]	XX (XX%)
	Did not complete [3]	XX (XX%)
Check that the subject / caregiver injects within 5 minutes of removing the needle cap.	n	XX
	Easily [1]	XX (XX%)
	With some difficulty [2]	XX (XX%)
	Did not complete [3]	XX (XX%)
Check that the subject / caregiver pinches the skin around the injection site. Inserts the entire needle into the pinched area at an angle.	n	XX
	Easily [1]	XX (XX%)
	With some difficulty [2]	XX (XX%)
	Did not complete [3]	XX (XX%)

[1] Subject / caregiver completed task easily without repeated reference to the IFU.

[2] Subject / caregiver completed task but with some difficulty or repeated reference to the IFU for assistance.

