- [3] I was not able to (or did not) complete task after multiple attempts and reference to the IFU.

userid: /arenv/arprod/compound/study/final/drivers/drivename.sas DDMMYYYY HH:MM

Example TAB_INJ4 (cont.)
 Protocol: MID205667
 Population: All Subjects (Safety)

Table X.X
 Summary of Subject Completed Checklist for At-Home Injection at Week 4

		Liquid Safety Syringe (N=XX)
Check expiration date on the safety syringe has not passed.	n	XX
	Easily [1]	XX (XX%)
	With some difficulty [2]	XX (XX%)
	Did not complete [3]	XX (XX%)
Look in the inspection window to check that the liquid is clear (free from cloudiness or particles) and colorless to slightly yellow in color.	n	XX
	Easily [1]	XX (XX%)
	With some difficulty [2]	XX (XX%)
	Did not complete [3]	XX (XX%)

- [1] I was able to complete the task easily without repeated reference to the IFU.
- [2] I was able to complete the task but with some difficulty or repeated reference to the IFU for assistance.
- [3] I was not able to (or did not) complete task after multiple attempts and reference to the IFU.

userid: /arenv/arprod/compound/study/final/drivers/drivername.sas DDMMYYYY HH:MM

Example TAB_INJ4 (cont.)
 Protocol: MID205667
 Population: All Subjects (Safety)

Table X.X
 Summary of Subject Completed Checklist for At-Home Injection at Week 4

		Liquid Safety Syringe (N=XX)
Remove the clear needle cap from the safety syringe by pulling it straight off.	n	XX
	Easily [1]	XX (XX%)
	With some difficulty [2]	XX (XX%)
	Did not complete [3]	XX (XX%)
Inject within 5 minutes of removing the needle cap.	n	XX
	Easily [1]	XX (XX%)
	With some difficulty [2]	XX (XX%)
	Did not complete [3]	XX (XX%)
Use your free hand to gently pinch the skin around the injection site. Insert the entire needle into the pinched area at an angle as shown.	n	XX
	Easily [1]	XX (XX%)
	With some difficulty [2]	XX (XX%)
	Did not complete [3]	XX (XX%)

- [1] I was able to complete the task easily without repeated reference to the IFU.
- [2] I was able to complete the task but with some difficulty or repeated reference to the IFU for assistance.
- [3] I was not able to (or did not) complete task after multiple attempts and reference to the IFU.

userid: /arenv/arprod/compound/study/final/drivers/drivername.sas DDMMYYYY HH:MM

Example TAB_INJ4 (cont.)
 Protocol: MID205667
 Population: All Subjects (Safety)

Table X.X
 Summary of Subject Completed Checklist for At-Home Injection at Week 4

		Liquid Safety Syringe (N=XX)

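### Full needle insertion, a critical step, shares one checklist item with pinching and angle, so success at the unobserved Week 4 dose can be misclassified in either direction

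*SAP*

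**What the plan says.** **Success definition.** Protocol 4.1 requires a correct site, a full dose, and no syringe finding that points to an incomplete dose. The full-dose criterion begins "Full dose administered: subject fully inserts the needle, slowly depresses the plunger until the stopper reaches the bottom of the syringe" and ends with needle-guard activation. Protocol 7.3 describes the critical steps in matching terms: "correct choice of injection site and a full dose administered (determined by the subject fully inserting the needle", followed by the plunger and needle-guard steps. Neither section lists pinching or angle. Of the home checklist, 7.3 says: "Failure to perform one of the critical steps will be deemed to be a failure to successfully administer the injection".

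**Checklist items.** The SAP is written on protocol amendment 1. Its in-clinic shell (TAB_INJ3) has one row for whether the user "pinches the skin around the injection site. Inserts the entire needle into the pinched area at an angle". The home shell (TAB_INJ4) has the matching row, "gently pinch the skin around the injection site. Insert the entire needle into the pinched area at an angle as shown". Each row takes one of three answers: easily, with some difficulty, or did not complete. The lowest answer in clinic means that the user "was not able to (or did not) complete task after multiple attempts and reference to the IFU, or intervention was required". At home it reads "I was not able to (or did not) complete task after multiple attempts and reference to the IFU".

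**How success is judged.** Under Protocol 4.1 the investigator decides. In clinic the basis is direct observation plus syringe inspection. At home it is the completed checklist plus inspection of the returned syringe. Protocol 6.8.2 adds that the subject is queried at Visit 4. The decision has its own field in TAB_INJ2 (yes, no, not attempted).

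**The concern.** One answer has to cover three actions, and only one of them is in the success definition. A home user who inserted the needle fully but did not pinch can truthfully mark the item as not completed, although the protocol's insertion criterion was met. A user who pinched and angled the syringe but inserted only part of the needle may still mark the item as easy. The investigator reading the form four weeks later cannot tell these cases apart from the answer alone, and no text says how a *did not complete* on the mixed item should be read.

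What is at stake is the Week 4 secondary endpoint, which is the study's only measure of use outside the clinic, and the two composites that include that dose (Weeks 4 and 8; Weeks 0, 4 and 8). The checklist summaries (Tables 7.3 and 7.4) are affected as well, because they cannot show how often the insertion step itself failed.

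**Working it through.** **Step 1. Match each full-dose step to its checklist row.**

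| Step in Protocol 4.1 and 7.3 | Row in TAB_INJ3 and TAB_INJ4 |
|---|---|
| Needle fully inserted | No row of its own; merged with pinch and angle |
| Plunger pushed slowly | Own row |
| Plunger pushed to the bottom | Own row |
| Thumb moved up (needle guard) | Own row |

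Insertion is the only full-dose step merged with elements outside the criteria. As background only, the amendment log shows that angle and pinched skin were removed from the criterion after a use-related risk review. This confirms that their absence from the current text is deliberate.

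**Step 2. List the evidence on insertion, dose by dose.**

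- *Weeks 0 and 8.* The investigator watches the injection and can separate a missed pinch from a partial insertion, whatever the form says.
- *Week 4, syringe.* Protocol 7.3 describes checking that the plunger is down and the needle has retracted. Neither sign shows how deep the needle went.
- *Week 4, Visit 4 query.* Protocol 6.8.2 plans it, about four weeks after the injection, but specifies no question on insertion.
- *Week 4, root-cause review.* Protocol 4.1 and 7.3 start it only once an injection is called unsuccessful. It may explain a false failure, but it cannot find a false success.
- *Week 4, user-error summary.* TAB_INJ2 as drafted lists autoinjector errors and has no needle-insertion category other than Other.

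The merged item is therefore the only specified record of insertion for that dose.

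**Step 3. Reproduce the plan's precision table.** Inputs: n = 50 (Protocol 9.2.2) and exact Clopper-Pearson limits (SAP 7.1). For x successes, the lower limit is the 0.025 quantile of Beta(x, n − x + 1) and the upper limit is the 0.975 quantile of Beta(x + 1, n − x). For 96%, x = 48, which gives 86.29 and 99.51; the table prints 86, 100. All 11 rows reproduce after rounding.

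**Step 4. Size per misclassified subject.** One subject moves the Week 4 proportion by 1/50 = 2.0 points, or 1/55 = 1.8 points if all 55 enrolled subjects attempt the dose. A composite moves by 1 divided by its own denominator, and only if that subject's other doses in the composite were successful.

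**Step 5. Range.** The documents give no count of misclassified injections, so k below is an assumption.

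False failures, n = 50, one true failure:

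| k | Successes | Observed | Exact 95% CI |
|---|---|---|---|
| 0 | 49/50 | 98% | 89, 100 |
| 1 | 48/50 | 96% | 86, 100 |
| 2 | 47/50 | 94% | 83, 99 |
| 3 | 46/50 | 92% | 81, 98 |
| 5 | 44/50 | 88% | 76, 95 |

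False successes work the other way. With three true failures (47/50 = 94%; 83, 99), one partial insertion passed as complete gives 48/50 = 96% (86, 100). If all three are passed, the result is 50/50 = 100% (93, 100).

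**The case against.** The strongest reply is that no checklist answer decides success. The investigator does, in a separate field, and Protocol 7.3 fails an injection for a missed critical step, not for the lowest answer on an item that also holds non-critical elements. Read literally, a skipped pinch with full insertion still meets the criteria, and the Visit 4 review is an opportunity to sort this out. That is right, and it limits the point: misclassification is possible, not automatic. It does not remove the point, because at home the investigator has no specified information with which to apply the rule.

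The evidence is also indirect. The checklists are in the SRM, which is not available here, and the mock shells are not dependable copies, since TAB_INJ2 carries autoinjector wording. Protocol 6.8.2 says the home form records the ease of each critical step, so the real form might separate insertion. This stands as a reason to check the SRM first. Still, both shells show the same merge.

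Mirroring an instruction step in one row is a legitimate choice in a descriptive study, and a separate item would reduce self-report error only in part. Both are fair and bear on the size of the gain.

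A reader might also infer that the primary endpoint is compromised. The documents do not support that, because the Week 8 injection is watched. A reader might call a missed pinch harmless, but the documents show only that it is not a success criterion.

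**Conclusion.** The point holds for the Week 4 secondary endpoint, the two composites that contain that dose, and the readability of Tables 7.3 and 7.4. For the home dose, a step that decides success is recorded only in combination with two actions that do not, and no other specified evidence separates them. Each misclassified subject shifts the Week 4 proportion by 2 points at n=50, in either direction. How many there would be is unknown. The tabulated range is for scale, and any assumed rate of skipped pinching would have no source in the plan.

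The conclusion assumes that the forms in the SRM match the shells and that the Visit 4 query does not routinely ask about insertion. If either assumption is wrong, the endpoint concern shrinks or disappears. A reader might go further and conclude that every *did not complete* on this item must be scored as a failed injection. Protocol 7.3 does not say so.

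**What to change.** First confirm the wording of both checklists in the SRM. If they match the shells, split the item in both checklists and in TAB_INJ3 and TAB_INJ4:

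- (a) pinched the skin and inserted at an angle: recorded, not a success criterion;
- (b) inserted the entire needle: critical.

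State in Protocol 7.3 that only (b) informs the success decision.

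If the home form can no longer change, add one eCRF field at the existing Visit 4 review for whether the entire needle was inserted, and use that field, not the combined item, for the Week 4 success judgement.

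The cost is one extra line per checklist and per shell, or one eCRF field, with no new visit or procedure. The downside is that the checklist would no longer follow the instruction step one-to-one. The Visit 4 fallback also relies on recall over about four weeks, so splitting the form is the better option where it is still possible.
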